6.2. Appendix 2: Changes to Protocol-planned Analyses

Following changes to protocol-planned analyses are reported in current SAP:

- Due to limited sample size in this study, some summaries planned by protocol will be replaced by listings of individual data.
- As stated in Section 5.7.1.1.2, a preliminary PK analysis will be carried out after 3 first participants, using the theoretical blood sampling times (planned time or scheduled time) and the validated concentration data.

6.3. Appendix 3: List of TFLs

The Table Of Contents (TOC) of Tables Figures and Listings (TFLs) will be provided in a separate document, as well as the shell TFLs and specifications.

In the TOC of TFLs, the outputs selected for TSC will be flagged.

6.4. Appendix 4: Disease Characteristics and demographics

All demographic data and baseline characteristics will be summarized in output tables in all participants from the SAF and the DDS (if different from the SAF), and presented in data listings for the SAF.

The Baseline Characteristics and demographics data are described in the Table 8 below:

Table 8: Baseline Characteristics and demographic data

Variable	Quantitative parameters	Qualitative parameters	Derived variable	SAF	DDS*
Country		X		X	X
Sex (M/F)		X		X	X
Race		X		X	X
Age (years)	X			X	X
Weight (kg)	X			X	X
Height (cm)	X			X	X
Body Mass Index (BMI) (kg/m ²)	X		X	X	X
ECOG performance status		X		X	X
Smoking history		X		X	X
BRAF V600E Mutation Result (Local)		X		X	X

*: If different from the SAF

Notes:

- The Age described in the table is the age reported in the eCRF.
- BMI will be calculated as weight(kg)/height²(m²)

6.5. Appendix 5: Cancer History

Cancer History will be summarized in participants from the SAF and the DDS (if different from the SAF). Cancer History will also be listed for the SAF.

Note:

- In case of missing initial diagnosis date or missing date of first metastasis, substituting rules defined in appendix 9 (Section 6.9.3) will be applied.

The Cancer History data are described in the Table 9 below:

Table 9: Cancer History data

Variable	Quantitative parameters	Qualitative parameters	Derived variable	SAF	DDS*
Diagnosis at study entry		X	X	X	X
Time since initial diagnosis (months) computed as [date of treatment assignment minus the date of initial diagnosis + 1]/30.4375	X		X	X	X
Primary tumor location		X		X	X
Delay between diagnosis of the primary tumor and metastasis (months)	X		X	X	X
Diagnosis method		X		X	X
Metastatic disease sites ("List of metastatic organs")		X		X	X
Number of metastatic organs (1, 2, >2)		X		X	X
Number of Prior Systemic Regimens in the metastatic setting	X			X	X

*: If different from the SAF

6.6. Appendix 6: Medical History, Baseline Signs and Symptoms

Medical history data will be coded using MedDRA dictionary (latest version in use) and summarized by SOC and PT with the number and percentage for the SAF. A by-participant listing of medical history information will be provided for the SAF. Medical history related to Covid-19 (SARS-CoV-2) will be identified during coding process using verbatim (by default when MH verbatim includes “COVID-19” as prefix), and will be flagged in the listing.

Incomplete dates will be handled as described in Appendix 9.

6.7. Appendix 7: Prior/concomitant/follow-up therapies

Medications will be coded using the latest version of the World Health Organization (WHO) Drug Dictionary (March 2021 Enhanced Dictionary Version Global B3 at set-up, and latest version in use for final analysis) and recorded on the “Prior Anti-Neoplastic Therapy – Medication “ and “Prior/Concomitant Medications” eCRF pages.

Medications used to treat Covid-19 (SARS-CoV-2) will be identified using WHODrug Standardised Drug Groupings (SDG) “Drugs for COVID-19”.

Therapeutic / Diagnostic Procedures (both prior and concomitant) will be coded using MedDRA dictionary (latest version in use) and recorded on the "Medical and Surgical Procedures" eCRF pages.

Prior anti-neoplastic surgeries will be coded similarly.

Procedures used to treat Covid-19 (SARS-CoV-2) will be flagged when the “Adverse Event ID linked to the procedure” or “Medical History ID linked to the procedure” is coded as related to Covid-19 (SARS-CoV-2), or when “COVID-19” words are located at any location inside the “Reason (Indication)” provided in CRF.

The SAF will be used to describe all Prior/concomitant/follow-up therapies summaries and listing, unless otherwise specified.

Where a medication start date is partially or fully missing, and it is unclear as to whether the medication is prior or concomitant, it will be assumed that it is concomitant.

6.7.1. Prior Therapies

Prior therapies are defined as any therapies starting and ending before the start of study treatment.

Prior therapies include:

- prior antineoplastic treatments
- prior medications (excluding prior anticancer treatments).
- prior diagnostic/therapeutic procedures (excluding prior anticancer treatments).

6.7.1.1. Prior Anticancer Therapy

Prior antineoplastic therapies will be classified in three separate categories: medications, radiotherapy, and surgery.

Sponsor Name: Pierre Fabre Médicament

Sponsor Protocol ID: W00090GE102

PII

Listings will be provided for each category separately (medication, radiotherapy, surgery) and presented in SAF, showing at least data detailed below:

- Prior antineoplastic therapy—medications:
 - Participant reported with medications (Yes/No)
 - Start Date/End Date
 - Drug Name
 - Anatomical Therapeutic Classification (ATC) code level 4 and Preferred Drug Name
 - Setting
 - Reason for discontinuation
 - Best overall response
 - Type of Treatment
 - Time from medication start to progression (months), using the “Date of Relapse/Progression” as collected in the medication form
 - Time from medication end to first intake (<1 month, 1-<6 months, 6-<12 months, >=12 months)
- Prior antineoplastic therapy - radiotherapy :
 - Participant reported with radiotherapy (Yes/No)
 - Start Date/End Date
 - Dose, Unit
 - Location/Site
 - Intent
 - Setting
 - Best Overall Response
 - Time from radiotherapy end to first intake (<1 month, 1-<6 months, 6-<12 months, >=12 months)
- Prior antineoplastic therapy – surgery (excluding biopsies):
 - Participant reported with prior surgeries (Yes/No)
 - Date
 - Site/Location
 - Result of Surgery
 - Treatment intent
 - SOC and PT
 - Time from surgery to first intake (<1 month, 1-<6 months, 6-<12 months, >=12 months)

Incomplete dates will be handled as described in Appendix 9 (Section 6.9.4).

Note:

- Time from last medication to progression will be derived if first intake date of last medication and PD dates are not completely missing. In that case, participant will be counted in the missing category. It will be computed in months as [date of PD - start date of last medication + 1] / 30.4375.
- Time from last medication to first intake (respectively time from last radiotherapy to first intake, time from last surgery to first intake) will be derived if last intake date of the last medication (respectively last radiotherapy date, last surgery date) is not completely missing. In that case, participant will be counted in the missing category. It will be computed in months as [date of first encorafenib administration - end date of last medication (resp. last radiotherapy, last surgery) + 1] / 30.4375.

6.7.1.2. Prior medications (excluding antineoplastic therapy)

Prior medications (excluding antineoplastic therapy) will be listed by ATC code level 4, Preferred Drug Name using the SAF, in the same listing as concomitant medications (see Section 6.7.2.2) and flagged as prior medications.

Incomplete dates will be handled as described in Appendix 9 (Section 6.9.2).

6.7.1.3. Prior Therapeutic / Diagnostic Procedures

Prior Therapeutic / Diagnostic Procedures (excluding prior anticancer treatments) will be listed by SOC and PT for the SAF, in the same listing as concomitant procedures (see Section 6.7.2.3) and flagged as prior procedures.

Incomplete dates will be handled as described in Appendix 9 (Section 6.9.2).

6.7.2. Concomitant therapies

Concomitant therapies are defined as any therapies starting on or after the start of study treatment but no later than 30 days (<30 days) after the last dose of study treatment or medications starting prior to the start of study treatment and continuing after the start of study treatment.

Concomitant therapies include:

- Concomitant antineoplastic therapies: radiotherapies
- Concomitant medications.
- Concomitant diagnostic/therapeutic procedures.

6.7.2.1. Concomitant Anticancer radiotherapies

Listing will be provided using the SAF. There will be no imputation for missing end dates.

6.7.2.2. Concomitant medications

Concomitant Medications will be summarized and listed by ATC code level 4 and Preferred Drug Name, using the SAF.

Of note, the listing will include all medications reported in the CRF form “Prior and Concomitant Medication”, regardless start date. Drugs started prior to first intake or during the follow up period will be identified. A flag to identify the medications used to treat Covid-19 (SARS-CoV-2) will also be included in the listing.

A summary table of Covid-19 (SARS-CoV-2) vaccines will be provided on SAF, with:

- Number and proportion of participants vaccinated. Participant analyzed as Vaccinated are participants having received at least one dose of a COVID-19 vaccine within 28 days before the 1st study drug administration, up to study discontinuation.
- Number and proportion of participants vaccinated with 1, 2, 3 doses. Participant analyzed as Vaccinated with X dose(s) means that he received X dose(s) within 28 days before the 1st study drug administration, up to study discontinuation.
- Summary of Covid-19 vaccines by ATC code level 4 and Preferred Drug Name. The selection of COVID (SARS-CoV-2) vaccines will be identified using WHODrug SDG “Vaccines for COVID-19” (narrow scope, ATC4 J07BX).

Incomplete dates will be handled as described in Appendix 9 (Section 6.9.2).

6.7.2.3. Concomitant Therapeutic / Diagnostic Procedures

A by-participant listing will be provided on the SAF including a flag to identify procedures used to treat Covid-19. Procedures started prior to first intake or during the follow up period will be identified.

6.7.3. Follow-up Medications

Any therapy started more than 30 days (≥ 30) after encorafenib last intake, will be included in the listing specified in section 6.7.2.2 (for medication) or 6.7.2.3 (for procedure).

6.8. Appendix 8: Protocol Deviations

All protocol deviations will be evaluated at least prior to database lock or any snapshot.

Protocol deviations and additional reasons of exclusion from analysis sets (such as missing primary criterion or insufficient exposure to the treatment due to premature withdrawal), will be described in the dedicated protocol deviations list based on TransCelerate PDAP template, separately from the statistical analysis plan and classified as important/non-important deviation before the first participant inclusion or prior to any snapshot.

A listing of all deviations and a listing of additional reasons of exclusion for statistical analysis will be provided for all assigned to treatment participants, including the type of impact (Important/Non important) as validated during the data review/ Validation Committee meeting.

Summary of protocol deviations will be provided on the SAF with:

- Number and percentage of participants with at least one deviation
- Number and percentage of participants with at least one important deviation, overall, then by category of deviations, then by description inside each category,
- Number and percentage of participants with at least one non-important deviation, overall, then by category of deviations

This table will be repeated for protocol deviations related to Covid-19 (SARS-CoV-2).

Protocol deviations related to Covid-19 (SARS-CoV-2) will be flagged in the data listing. Otherwise specified, protocol deviations related to Covid-19 (SARS-CoV-2) will be identified when prefix “COVID-19” is used in the deviation description.

6.9. Appendix 9: Missing Values – Missing Visits

For partially missing dates for efficacy endpoints, the following imputation rules will be used: if the day of the month is missing, but month and year are known (UN-MMM-YYYY), it will be imputed by the 1st of the month (01-MMM-YYYY). If this implementation rule produces a date before start of treatment, then the date of start of treatment is used.

6.9.1. Adverse Events

In case of missing information for AEs, this will be treated as described in Section 5.6.2.

For partial AE start dates or completely missing AE start dates, the date imputation will be based on the temporal relation between the partial date and the treatment start date as detailed in the Table 10 below. No imputation will be performed when the year is missing for the start date.

Table 10: AE Start Date Imputation Example Scenarios

Partial AE start date	Treatment start date	Temporal relationship compared to treatment start	Imputed Date
12mmYYYY	20OCT2001	Uncertain	<blank>
ddmmmm2000	20OCT2001	Before	01JUL2000
ddmmmm2001	20OCT2001	Uncertain	20OCT2001
ddmmmm2002	20OCT2001	After	01JAN2002
ddSEP2001	20OCT2001	Before	15SEP2001
ddOCT2001	20OCT2001	Uncertain	20OCT2001
ddNOV2001	20OCT2001	After	01NOV2001

For missing or partially missing stop dates of AE, the imputation date will be based on the temporal relation between the partial date, the last contact date and the 30-day safety follow-up date as detailed in the Table 11 below:

Table 11: End Date Imputation Example Scenarios

Partial end date (assumes that “ongoing” is not ticked)	Minimum (Last contact date, 30-day FU date)	Ongoing	Imputed Date
Missing	20OCT2001	No	20OCT2001
ddmmmm2000	20OCT2001	No	31DEC2000
ddmmmm2002	20OCT2001	No	31DEC2002
ddmmmm2001	20OCT2001	No	20OCT2001
ddSEP2001	20OCT2001	No	30SEP2001
ddOCT2001	20OCT2001	No	20OCT2001

Sponsor Name: Pierre Fabre Médicament

Sponsor Protocol ID: W00090GE102

PII

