8.4. Adverse Events and Serious Adverse Events

Adverse events and SAEs are defined in Appendix 10.8. Events meeting these definitions are also specified.

8.4.1. Time Period and Frequency for Collecting Adverse Event and Serious Adverse Event Information

All adverse events will be collected from when the participant first provides informed consent until the 30-day safety follow-up visit. If the investigator learns of any SAE, including a death, at any time after a participant has been discharged from the study and he/she considers the event to be related to the study treatment or study participation, the investigator must promptly notify the sponsor.

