5.6.2. Adverse Events

The occurrence of an AE is defined by the appearance of a new single event, the reappearance of a previously recovered event or the worsening of a continuous event (relative to its previous status).

AEs will be coded using Medical Dictionary for Regulatory Activities (MedDRA) (latest version in use).

A TEAE is defined as any event that first occurred or worsens from the first study treatment administration date up to the last administration date + 30 days (inclusive). As conservative approach, if year of AE start is missing, and when end date is missing or \geq first administration date, AE will be considered as a TEAE.

A participant with more than one occurrence of the same adverse event in a particular System Organ Class (SOC) will be counted only once in the total of those experiencing adverse events in that particular SOC.

If a participant experiences the same adverse event at more than one severity, or with more than one relationship to encorafenib, the most severe rating or the stronger causal relationship to encorafenib will be given precedence.

The denominator used to calculate incidence percentages consists of participants in the SAF.

AEs will be grouped by SOC and Preferred Term (PT) and sorted in descending frequency.

For tables by NCI CTCAE grade, if a participant has more than one AE, the worst grade will be summarized.

Sponsor Name: Pierre Fabre Médicament

Sponsor Protocol ID: W00090GE102

PII

Following summaries with number and percentage of participants will be presented:

- Summary of AE (Overall, Related, Grade 3+, Related Grade 3+):
 - AEs,
 - TEAEs,
 - Serious TEAE,
 - TEAE by severity grade,
 - TEAE leading to discontinuation of encorafenib regardless of causality,
 - TEAEs leading to encorafenib dose modification (interruption or reduction),
 - TEAEs leading to encorafenib Drug interruption,
 - TEAEs leading to encorafenib dose reduction,
 - TEAEs requiring additional therapy,
 - TEAE last outcome,
 - TEAE last action taken with encorafenib.
- Summary of SAEs (Overall, Related, Grade 3+, Related Grade 3+):
 - SAEs,
 - Serious TEAEs,
 - Serious TEAE by severity grade,
 - Serious TEAE leading to discontinuation of encorafenib regardless of causality,
 - Serious TEAEs leading to encorafenib dose modification (interruption or reduction),
 - Serious TEAEs leading to encorafenib Drug interruption,
 - Serious TEAEs leading to encorafenib dose reduction,
 - Serious TEAEs requiring additional therapy,

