6.9.2. Prior and Concomitant Medication

In case of missing or partially missing start dates (resp. stop date) for prior/concomitant medication, same rules as those described in Table 10 (resp. Table 11) for AE will be applied.

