6.9.4. Antineoplastic therapies

Prior Antineoplastic therapies

Incomplete start dates will be handled by applying the same imputation rules as described for AE/concomitant medications start date (Sections 6.9.1 and 6.9.2) except:

- If only day is missing, and month and year match that of the treatment start date, impute as first dose of study -1;
- If both day and month are missing, and the year matches that of the treatment start date, then impute as date of first dose of study drug - 1.

Completely missing start date is imputed as date of first dose of study drug - 1;

Incomplete end dates and dates of progression on the prior antineoplastic therapies will be handled using the following rule:

- If only day is missing, imputed date = min (date of first dose of study drug -1, last day of the month);
- If both month and day are missing, imputed date = min (date of first dose of study drug -1, 31DEC).
- If the end date or the date of progression is not missing and the imputed start date is after the end date or after the date of progression, use the min (end date, date of progression) as the imputed start date.

Post-treatment therapies:

If any, it will be reported as part of the concomitant medications, and handled as specified in Section 6.9.2.

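### The SAP imputes a partial AE start date in the month or year of first dose without checking the end date, so an event known to have ended before dosing can be counted as treatment-emergent

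*SAP*

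**What the plan says.** SAP section 6.9.1 states that for partial or missing AE start dates "the date imputation will be based on the temporal relation between the partial date and the treatment start date". Table 10 illustrates this with a first dose on 20OCT2001. When only the day is missing and the month is that of first dose, the row reads "ddOCT2001 20OCT2001 Uncertain 20OCT2001". When day and month are missing and the year is that of first dose, it reads "ddmmmm2001 20OCT2001 Uncertain 20OCT2001". The table has no end-date column and no end-date condition. For a missing year the rule is "No imputation will be performed when the year is missing for the start date".

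SAP section 5.6.2 gives the classification: "A TEAE is defined as any event that first occurred or worsens from the first study treatment administration date", up to 30 days after the last dose. It adds a default for a missing start year: the event is treatment-emergent if its end date is missing or is not before first dose. That is the only AE end-date check in the SAP.

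Protocol section 8.4.1 sets the collection period: "All adverse events will be collected from when the participant first provides informed consent until the 30-day safety follow-up visit". SAP section 1.2.1 puts screening in the 28 days before first dose.

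Two other imputation rules bear on this. For prior antineoplastic therapies, section 6.9.4 deals with an imputed start that falls after a known end or progression date: "use the min (end date, date of progression) as the imputed start date". For prior and concomitant medications, section 6.9.2 says "same rules as those described in Table 10 (resp. Table 11) for AE will be applied", with no such cap.

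**The concern.** Setting an uncertain start to the first-dose date is a sensible conservative rule when the data leave it open whether the event began before or after dosing. It stops being conservative when the end date settles the question. An AE that ended before first dose cannot be treatment-emergent, whatever day it began. Table 10 ignores that information and produces a start date later than the end date.

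The SAP handles the neighbouring cases correctly. With the start year missing, the end date is consulted. For prior cancer therapies, the imputed start is capped. The gap is the middle case, an AE with a known start year, where there is more information than in the missing-year case but the result is worse.

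What is at stake is TEAE incidence, a secondary endpoint, in a study of three to six evaluable participants where one person moves a percentage a long way. Serious TEAEs also go to the Trial Steering Committee's tolerability assessment (SAP section 5.8.1).

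**Working it through.** **Step 1: reproduce Table 10.** Coding the table as a function of the partial start date and the first-dose date alone returns the SAP's result in all seven rows. No end date is needed, which confirms that it is not an input.

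**Step 2: apply the rule to records with a known end date.** First dose is 20OCT2001, as in Table 10. Duration = end − imputed start + 1. An event is counted as treatment-emergent if its imputed start is on or after first dose.

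| Partial start | Known end | Imputed start | Duration (days) | TEAE as written |
|---|---|---|---|---|
| ddOCT2001 | 10OCT2001 | 20OCT2001 | 10 − 20 + 1 = −9 | Yes |
| ddmmmm2001 | 30SEP2001 | 20OCT2001 | −20 + 1 = −19 | Yes |
| ddOCT2001 | 25OCT2001 | 20OCT2001 | 25 − 20 + 1 = 6 | Yes |
| Year missing | 10OCT2001 | none | not defined | No (section 5.6.2) |

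The first two rows are wrong: those events ended 10 and 20 days before dosing. Both end dates lie within 28 days of first dose, so both could be genuine screening events. The third row is the case for which the rule is suitable. The fourth is the first record with less information, and it is classified correctly.

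**Step 3: add an end-date cap**, imputed start = min(Table 10 date, AE end date).

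| Partial start | Known end | Capped start | Duration (days) | TEAE |
|---|---|---|---|---|
| ddOCT2001 | 10OCT2001 | 10OCT2001 | 1 | No |
| ddmmmm2001 | 30SEP2001 | 30SEP2001 | 1 | No |
| ddOCT2001 | 25OCT2001 | 20OCT2001 | 6 | Yes |

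The wrong rows are corrected and the valid one is unchanged.

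**Step 4: how much of the screening window the rule covers.** For a 20 October first dose, 19 of the 28 preceding days are in the same month and all 28 in the same year. Now assume a first dose equally likely on any date in 2022, giving 365 × 28 = 10,220 pairs of dosing date and screening day. Pairs in the same month number 7 × 462 + 4 × 434 + 378 = 5,348 (months of 31, 30 and 28 days), or 52%. Pairs in different years number 28 × 29 / 2 = 406, so 96% share the year. These are shares of days within reach of the rule. They do not estimate how many records have a partial date, and the documents give no figure for that.

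**Step 5: effect on a TEAE row.** One participant wrongly counted adds 1/N, where N is the Safety Set. For N = 3 this is 33.3 percentage points; for N = 6 it is 16.7. The Safety Set is everyone dosed (SAP section 4.1), and non-evaluable participants are replaced (SAP section 1.2), so N can exceed the evaluable number: 1/4 = 25.0 points or 1/7 = 14.3 points with one replacement. If that participant has a genuine TEAE in the same row, the increase is zero.

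**The case against.** Much of the case on the other side stands.

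- **Rarity.** The record must start and end between consent and first dose, have an unknown start day, and have an end known to precede dosing. Protocol section 8.4.2 requires onset and end dates, and the data-cleaning and lock procedures (Protocol section 10.1.8.3) query gaps. A missing month is less plausible still for events collected prospectively.
- **Consequence.** DLTs come from a CRF flag (SAP section 5.3.1), nothing is tested, and all data are listed, so an impossible date could be seen by eye. Any error over-counts TEAEs, the cautious direction in a tolerability study.
- **Room in the wording.** Table 10 is titled as example scenarios, and programming specifications sit in a separate document. A programmer might add the check, and an event that ended before dosing does not meet the TEAE definition on its facts. But no end-date check is stated for known-year dates, and section 6.9.1 says expressly what the imputation depends on. This lowers the likelihood of an error without removing the gap.

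A reader might infer three stronger things that the documents do not support. The first is that finished prior medications necessarily become concomitant because section 6.9.2 borrows Table 10. Section 6.7 assumes concomitant use only where status is unclear, and section 6.7.1 defines prior therapies as ending before treatment. A medication known to have stopped before dosing is not unclear. What is left is mainly an impossible imputed date, which sits badly with the definition of concomitant therapy in section 6.7.2.

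The second is that every such AE adds 33 points. Protocol section 2.1.4 reports alopecia in 56%, palmar-plantar erythrodysesthesia in 52% and arthralgia in 44% on this dose, so most participants are likely to have a genuine TEAE and the any-TEAE row would probably not move.

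The third is that the primary endpoint is at risk. The CRF flag rules that out for practical purposes.

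**Conclusion.** The point holds in a limited form. For an AE whose start is partial but falls in the month or year of first dose, and whose end is known to precede first dose, the SAP's stated rule gives a start after the end and counts the event as treatment-emergent. It is a rule that yields a wrong answer for that case, and it is inconsistent with how sections 5.6.2 and 6.9.4 treat similar records.

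The size is small. Only secondary TEAE summaries are affected, including serious TEAEs. The number of such records cannot be estimated from the documents and is probably very low. The 33-point and 17-point figures are maxima: they assume a Safety Set of exactly three or six and no genuine TEAE for that participant in that row. The conclusion also assumes that the programming follows section 6.9.1 as written. This is a worthwhile correction rather than a threat to the study's conclusions.

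**What to change.** Add to SAP section 6.9.1, below Table 10:

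> *The first-dose date is imputed only if the AE end date is missing or on/after first dose. If the end date (known, or partial but clearly before first dose) precedes first dose, the imputed start date may not be later than the end date and the event is not treatment-emergent.*

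In section 6.9.2, apply the same end-date cap, so that an imputed medication start cannot fall after its stop date and the dates agree with the prior and concomitant definitions in section 6.7.

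The cost is a sentence in each section and about one line of code. Both devices are already in the SAP: the end-date check in section 5.6.2 and the cap in section 6.9.4. Records with a missing end date, or an end on or after first dose, keep the present conservative handling.
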